to induce a number of severe and sometimes irreversible side effects, such as osteoporosis, diabetes, Cushing's syndrome, glaucoma, and muscle wasting (Schäcke et al, 2002, Rizzo et al, 2006). For local ocular administration, GCs exhibit a variety of effect/side effect rations, with the primary adverse events (AEs) of concern being elevation of intraocular pressure (IOP), cataract formation, and increased vulnerability to superinfection (Wang et al, 2009, Kersey et al, 2006, Rizzo et al, 2006). All currently marketed ophthalmic steroids carry the warning that use for longer than 14 days should only be carried out under close physician supervision, and it is generally recommended that the dose be tapered slowly over several days (Rizzo et al, 2006).

Dexamethasone, one of the most powerful GCs, is already marketed in the US as a sterile ophthalmic solution for the treatment of "steroid responsive inflammatory conditions of the palpebral and bulbar conjunctiva, cornea, and anterior segment of the globe, such as allergic conjunctivitis...". While dexamethasone and other GCs are presumed to be the most clinically effective in the treatment of late-phase inflammatory allergic reactions, their well known safety limitations for long-term use prohibit wide-spread adoption of this treatment.

Use of the OTX-DP seasonally creates a low, tapered, consistent dose of dexamethasone, possibly minimizing or possibly eliminating negative side effects of general topical ophthalmic GC use, while retaining its anti-inflammatory effects that may be particularly beneficial in the treatment of latephase ocular allergy.

One Phase 2, multicenter, prospective, randomized, double-masked vehicle controlled study in 68 subjects was completed utilizing the modified Ora-CAC® model. The study evaluated the safety and efficacy of OTX-DP as a sustained release drug depot for the treatment of the signs and symptoms of chronic allergic conjunctivitis. At 2 weeks, 4 weeks and 6 weeks after insertion of the OTX-DP, subjects underwent a series of 4 CACs over a period of 48 hours followed by clinical evaluation of the signs and symptoms of chronic allergic conjunctivitis. The co-primary efficacy endpoints were ocular itching and conjunctival redness at 14 days after

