#### 2 Months

- immunotherapeutic agents (treatment must have been maintained steadily for at least 2 months; neither the immunotherapeutic agent nor its dosage may change during the clinical study)
- 7. have a congenital or ocular anomaly (including punctal or lid ectropion, entropion, trichiasis, or supernumerary puncta) or anomalies of the punctum (including lack of good punctal apposition in both eyes);
- 8. have a diagnosis of any significant uncontrolled illness;
- 9. history of alcohol or drug abuse in the past year;
- 10. known history of moderate to severe allergic asthmatic reactions to any of the study allergens;
- 11. have planned surgery (ocular or systemic) during the trial period or within 30 days after;
- 12. have used an investigational drug or medical device within 30 days of the study or be concurrently enrolled in another investigational product trial;
- 13. be a female who is currently pregnant, planning a pregnancy, or lactating;
- 14. have a score of >0 for ocular itching and/or >1 for conjunctival redness prior to the challenge in either eye at Visit 2;
- 15. have an intraocular pressure that is less than 5 mmHg or greater than 22 mmHg or any type of glaucoma at Visit 2;
- 16. have had a history of an IOP increase as a result of steroid treatment;
- 17. have an unsuccessful transient punctum dilation to 0.7 mm prior to insertion of OTX-DP or PV;
- 18. be an employee of the site that is directly involved in the management, administration, or support of the study, or are an immediate family member of the same.

CLN-Protocol-0052 Page **24** of **61** 

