8.3 Definition of Baseline

For all efficacy variables , baseline will refer to the time specific measure at Visit 4a (e.g., ocular itching at 3 minutes post-CAC at Visit 4a will be the baseline for ocular itching at 3 minutes post-CAC at Visits 6b, 6a, 5, 8b, 8a, and 7).

For all safety variables, baseline is defined as the last measurement prior to the first dose of study medication.

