8.4 Data Analysis Conventions

Final data analysis will be performed by SDC after the study is completed and the database has been locked and released for unmasking. Statistical programming and analyses will be performed using SAS[®] version 9.4 or higher. Output will be provided in rich text format (RTF) for tables and portable document format (PDF) for tables, listings, and figures using landscape orientation. All study data will be listed by subject, treatment, and visit (as applicable) based on all randomized subjects unless otherwise specified.

Summaries for continuous and ordinal variables will include the number of observations (n), arithmetic mean, standard deviation (SD), median, minimum, and maximum. Minima and maxima will be reported with the same precision as the raw values; means and medians will be presented to one additional decimal place than reported in the raw values. Standard deviations will be presented to two additional decimal places than reported in the raw values. Summaries for discrete variables will include counts and percentages. All percentages will be rounded to one decimal place (i.e., XX.X%). Differences between active treatment groups and placebo will be calculated as active minus placebo and change from baseline will be calculated as follow-up visit minus baseline.

All statistical tests will be two-sided with a significance level of 0.05 (α = 0.05) unless otherwise specified. Confidence intervals (CIs) for differences between treatment groups will be two-sided at 95% confidence. All p-values will be rounded to 4 decimal places; p-values less than 0.0001 will be presented as "<0.0001"; p-values greater than 0.9999 will be presented as ">0.9999."

Unless otherwise specified, summaries will be presented by treatment group and, where appropriate, visit. Listings will be sorted by treatment group, subject number, visit/time point, and parameter as applicable.

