13.4 Intraocular Pressure (IOP)

Intraocular pressure will be assessed post-CAC by contact tonometry in each eye at Visits 2 (Day -5), 6b (Day 8), 8b (Day 15; 8 hours post Visit 8a), 9 (Day 30). The assessment is performed post-CAC for visits when the CAC is administered. Results will be taken from a single measurement and will be recorded in mmHg.

The observed IOP and change from baseline will be summarized using continuous descriptive statistics by visit, treatment group, and eye for the Safety population. The number of instances where IOP \geq 30 mmHg and increases 10 mmHg over baseline will also be summarized using counts and percentages.

A subject listing of IOP will also be produced.

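### SAP 13.4: read as one joint criterion, the IOP threshold count leaves out rises of 10 mmHg or more that end below 30 mmHg; report the two figures separately

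*SAP*

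**What the plan says.** SAP 13.4 is the only place in either document that sets IOP thresholds for analysis. It plans three outputs:

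- **Continuous summaries.** "The observed IOP and change from baseline will be summarized using continuous descriptive statistics by visit, treatment group, and eye for the Safety population". SAP 8.4 gives their content: "Summaries for continuous and ordinal variables will include the number of observations (n), arithmetic mean, standard deviation (SD), median, minimum, and maximum".
- **A threshold count.** The number of instances with IOP at or above "30 mmHg and increases 10 mmHg over baseline will also be summarized using counts and percentages".
- **Individual values.** "A subject listing of IOP will also be produced".

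SAP 8.3 defines the reference value: "For all safety variables, baseline is defined as the last measurement prior to the first dose of study medication". The only IOP reading scheduled before insertion is at Visit 2 (Protocol Appendix A), and Protocol 8.2 labels it baseline. Exclusion criterion 15 in Protocol 5.5.3 bars anyone found to "have an intraocular pressure that is less than 5 mmHg or greater than 22 mmHg or any type of glaucoma at Visit 2".

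SAP 8.1 makes the eye the unit of analysis for safety variables. Protocol 10.11 asks only for descriptive IOP summaries and gives no threshold.

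**The concern.** In the threshold sentence, IOP governs two conditions joined by a single *and* inside one clause. A programmer would naturally code this as a joint flag. With entry IOP capped at 22 mmHg, a joint flag is in effect a count of readings at or above 30 mmHg. The rise condition never brings in a case of its own, and at the two highest baselines it only takes cases out.

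The sentence also gives no operator before the 10, no denominator for the percentages, and no rule for an eye that qualifies at more than one visit. Neighbouring sections are more exact. SAP 13.2 counts subjects losing 10 or more letters, and SAP 13.3 and 13.5 state the base for their percentages.

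This matters because the product releases a steroid into the eye. Protocol 4.2 puts raised IOP first among the adverse effects of concern for locally given ocular glucocorticoids. Safety has no inferential testing (SAP 13), so this count is the only prespecified comparison of arms on an IOP threshold.

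**Working it through.** The plan states no figure to reproduce here. The check is to apply the rule across the eligible baselines.

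**Inputs**
- Baseline B: 5 to 22 mmHg in whole mmHg (Protocol 5.5.3, criterion 15; Visit 2 reading).
- Level: IOP of at least 30 mmHg (SAP 13.4).
- Rise: 10 mmHg (SAP 13.4), taken as at least 10. This is an assumption, because the SAP gives no operator. A rise of exactly 10 would need B + 10 ≥ 30, so B ≥ 20, and nobody with a lower baseline could ever be counted. That is unlikely to be intended.

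**Joint reading.** An instance counts if IOP ≥ max(30, B + 10). The smallest rise that counts is max(30 − B, 10). Rises of at least 10 that stay uncounted because IOP is below 30 run from 10 to 29 − B, which is an empty range once B reaches 20. Readings of at least 30 that stay uncounted because the rise is below 10 run from 30 to B + 9, which is an empty range until B reaches 21.

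| Baseline (mmHg) | Lowest IOP counted | Smallest rise counted | Rises ≥ 10 not counted | IOP ≥ 30 not counted |
|---|---|---|---|---|
| 5 | 30 | 25 | 10–24 | none |
| 10 | 30 | 20 | 10–19 | none |
| 15 | 30 | 15 | 10–14 | none |
| 18 | 30 | 12 | 10–11 | none |
| 19 | 30 | 11 | 10 | none |
| 20 | 30 | 10 | none | none |
| 21 | 31 | 10 | none | 30 |
| 22 | 32 | 10 | none | 30–31 |

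Example: 15 to 28 mmHg is a rise of 28 − 15 = 13. It passes the rise condition and fails the level condition, so it is not counted.

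**Two-count reading.** One tally takes IOP ≥ 30 and the other takes rises ≥ 10. Nothing in the last two columns is then left out.

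**Denominator.** Post-insertion IOP is scheduled at Visits 6b, 8b and 9, in both eyes. With the planned 40 subjects per arm, the base could be 40 subjects, 40 × 2 = 80 eyes, or 80 × 3 = 240 eye-visits. One eye qualifying at one visit is then 1/40 = 2.5%, 1/80 = 1.25% or 1/240 = 0.42%. Each is a defensible reading of instances with percentages, and the SAP does not choose.

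**The case against.** **The sentence may mean two counts.** It does not say that both parts must hold, and *increases* can be read as a noun: instances of IOP at or above 30 mmHg, and increases of 10 mmHg. Neither the title of Table 14.3.4 nor Protocol 10.11 settles it. This stands. The joint reading is the plainer one but is not certain, and if two counts are meant, the omissions in the table disappear. The SAP would still need to say so.

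**Nothing is lost from the report.** A rise from 15 to 28 mmHg enters the change-from-baseline summary as 13, and appears as the maximum if it is the largest. It is also in the listing, and in the ocular adverse event tables if the investigator reports it as an event. This stands too. A reader might infer that such rises would be hidden, and the documents do not support that. What is missing is narrower. A maximum shows one extreme per visit, arm and eye, not how many eyes crossed a level. A listing does not tabulate arms against each other. The protocol gives no IOP value that makes a rise an adverse event.

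**The unit is already set.** SAP 8.1 makes it the eye. That answers part of the denominator question, but not repeat counting across visits or the base for the percentages.

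**The count is a supplement.** The protocol does not ask for it, and no endpoint or decision rule depends on it. This is correct and limits the weight of the point.

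**Conclusion.** The point holds as a defect in one safety table. On the plain reading of SAP 13.4, rises of 10 mmHg or more ending below 30 mmHg go uncounted at every eligible baseline under 20 mmHg, and a few readings of 30 or 31 mmHg go uncounted at baselines 21 and 22. The size of the gap depends on baseline: rises of 10 to 19 mmHg at baseline 10, none at baseline 20. Only the categorical count by arm is affected.

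This rests on the joint reading, on taking the rise as at least 10 mmHg, and on the Visit 2 limits applying to each eye.

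Two stronger conclusions are tempting but unsupported. One is that the flag would miss most subjects with an IOP response. The documents give no distribution of baseline IOP or of rises, so no share can be stated. The other is to size the problem from the 6% with increased IOP in Protocol 4.2. That is an adverse-reaction rate after cataract surgery, not a threshold count in allergic conjunctivitis. This trial also excludes people with glaucoma or an earlier steroid-related IOP rise (criteria 15 and 16).

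**What to change.** Reword the threshold sentence in SAP 13.4 and set up Table 14.3.4 to show, by arm:

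1. increase from baseline ≥ 10 mmHg;
2. IOP ≥ 30 mmHg;
3. both together, if the sponsor wants to keep that row.

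State in the text whether the denominator is eyes or subjects. If it is subjects, say how the two eyes combine, for example by the worse eye. State whether counts are given per visit, at any post-insertion visit, or both, so that an eye qualifying at several visits is handled in one known way.

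Both figures are the SAP's own, and no new clinical threshold is proposed. With both rows shown, every rise of 10 mmHg or more and every reading of 30 mmHg or more is counted at all baselines from 5 to 22 mmHg, whichever reading was intended.

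The cost is one reworded SAP passage and two table rows, using readings already planned. It is best done before database lock and unmasking.

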13.5 Dilated Fundoscopy Examination

A dilated fundoscopy examination of the vitreous, optic nerve, macula, retina, and choroid will be performed at Visit 2 (Day -5) post-CAC and Visit 9 (Day 30). The assessment is performed post-CAC for visits when the CAC is administered. The results will be graded as normal, abnormal NCS, or abnormal CS.

The results will be summarized using counts and percentages for each treatment group and for the Safety population at each visit for each eye. The number and percentage of subjects showing a worsening from baseline will be presented for the following categories:

- Normal to Abnormal (NCS)
- Normal to Abnormal (CS)
- Abnormal (NCS) to Abnormal (CS)

Percentages will be based on the number of subjects in each treatment group with responses.

A subject listing of the dilated fundoscopy parameters will also be produced.

14. Interim Analyses

No interim analysis is planned.

15. Changes from Protocol-Stated Analyses

There are no changes from the protocol-stated analyses.

16. Revision History

Documentation of revision to the SAP will commence after approval of the final version 1.0.

17. Tables

Tables that will be included in the topline delivery are shown in boldface font.

Table Number	Title	Population
14.1.1	Subject Disposition	ITT Population
14.1.2	Demographics	ITT Population
14.1.3.1	Ocular Medical History	ITT Population
14.1.3.2	Non-Ocular Medical History	ITT Population
14.1.4.1	Ocular Prior and Concomitant Medications	ITT Population
14.1.4.2	Non-Ocular Prior and Concomitant Medications	ITT Population
14.1.5.1	Test Article Insertion and Removal	Safety Population
14.1.5.2	Test Article Visualization	Safety Population
14.1.5.3	Punctum Size Assessment	Safety Population
14.1.5.4	Exposure to Test Article	Safety Population
14.2.1.1	Ocular Itching – Primary Timepoints	ITT Population with Multiple Imputation (MCMC)
14.2.1.2	Ocular Itching	ITT Population with Multiple Imputation (MCMC)
14.2.1.3	Ocular Itching	ITT Population with LOCF
14.2.1.4	Ocular Itching	ITT Population with BOCF
14.2.1.5	Ocular Itching	ITT Population with WCO
14.2.1.6	Ocular Itching	ITT Population with Observed Data Only

14.2.1.7	Ocular Itching	PP Population with Observed Data Only
14.2.2.1	Conjunctival Redness	ITT Population with Observed Data Only
14.2.2.2	Conjunctival Redness	PP Population with Observed Data Only
14.2.3.1	Ciliary Redness	ITT Population with Observed Data Only
14.2.3.2	Ciliary Redness	PP Population with Observed Data Only
14.2.4.1	Episcleral Redness	ITT Population with Observed Data Only
14.2.4.2	Episcleral Redness	PP Population with Observed Data Only
14.2.5.1	Chemosis	ITT Population with Observed Data Only
14.2.5.2	Chemosis	PP Population with Observed Data Only
14.2.6.1	Eyelid Swelling	ITT Population with Observed Data Only
14.2.6.2	Eyelid Swelling	PP Population with Observed Data Only
14.2.7.1	Tearing/Watery Eyes	ITT Population with Observed Data Only
14.2.7.2	Tearing/Watery Eyes	PP Population with Observed Data Only
14.2.8.1	Rhinorrhea	ITT Population with Observed Data Only
14.2.8.2	Rhinorrhea	PP Population with Observed Data Only
14.2.9.1	Nasal Pruritus	ITT Population with Observed Data Only
14.2.9.2	Nasal Pruritus	PP Population with Observed Data Only
14.2.10.1	Ear or Palate Pruritus	ITT Population with Observed Data Only
14.2.10.2	Ear or Palate Pruritus	PP Population with Observed Data Only
14.2.11.1	Nasal Congestion	ITT Population with Observed Data Only
14.2.11.2	Nasal Congestion	PP Population with Observed Data Only
14.2.12.1	Nasal Composite Score – Qualitative	ITT Population with Observed Data Only
14.2.12.2	Nasal Composite Score – Qualitative	PP Population with Observed Data Only
14.2.12.3	Nasal Composite Score – Quantitative	ITT Population with Observed Data Only
14.2.12.4	Nasal Composite Score – Quantitative	PP Population with Observed Data Only
14.3.1.1	Overall Adverse Event Summary	Safety Population
14.3.1.2	All Ocular Adverse Events	Safety Population
14.3.1.3	All Non-Ocular Adverse Events	Safety Population
14.3.1.4	All Ocular Adverse Events Suspected to be Related to Investigational Product	Safety Population
14.3.1.5	All Non-Ocular Adverse Events Suspected to be Related to Investigational Product	Safety Population
14.3.1.6	All Ocular Serious Adverse Events Suspected to be Related to Investigational Product	Safety Population
14.3.1.7	All Non-Ocular Serious Adverse Events Suspected to be Related to Investigational Product	Safety Population
14.3.1.8	All Ocular Adverse Events by Severity	Safety Population
14.3.1.9	All Non-Ocular Adverse Events by Severity	Safety Population

14.3.1.10	All Ocular Adverse Events by Relationship to IP	Safety Population
14.3.1.11	All Non-Ocular Adverse Events by Relationship to IP	Safety Population
14.3.2	Visual Acuity (logMAR)	Safety Population
14.3.3	Slit-Lamp Biomicroscopy and Punctum Examination	Safety Population
14.3.4	Intraocular Pressure (mmHg)	Safety Population
14.3.5	Dilated Fundus Examination	Safety Population

18. Listings

Listing Number	Title	Population
16.1.7	Randomization Schedule	ITT Population
16.2.1	Subject Disposition	ITT Population
16.2.2.1	Protocol Deviations	ITT Population
16.2.2.2	Inclusion, Exclusion, and Procedural Exclusion Criteria	All Subjects
16.2.3	Subjects Excluded from the Per Protocol Population	ITT Population
16.2.4.1	Demographics	ITT Population
16.2.4.2	Ocular Medical History	ITT Population
16.2.4.3	Non-Ocular Medical History	ITT Population
16.2.4.4	Prior and Concomitant Ocular Medications	ITT Population
16.2.4.5	Prior and Concomitant Non-Ocular Medications	ITT Population
16.2.4.6	Allergic Skin Test	ITT Population
16.2.4.7	Punctum Size Assessment	ITT Population
16.2.5.1	Test Article Insertion	ITT Population
16.2.5.2	Test Article Visualization	ITT Population
16.2.5.3	Test Article Removal	ITT Population
16.2.5.4	Relief Medication Instillation	ITT Population
16.2.5.6	Conjunctival Allergen Challenge	ITT Population
16.2.6.1	Ocular Itching	ITT Population
16.2.6.2	Conjunctival Redness	ITT Population
16.2.6.3	Ciliary Redness	ITT Population
16.2.6.4	Episcleral Redness	ITT Population
16.2.6.5	Chemosis	ITT Population
16.2.6.6	Eyelid Swelling	ITT Population
16.2.6.7	Tearing	ITT Population
16.2.6.8	Nasal Symptoms	ITT Population
16.2.7.1	Adverse Events	ITT Population
16.2.7.2	Serious Adverse Events – Part 1	ITT Population
16.2.7.2	Serious Adverse Events – Part 2	ITT Population

16.2.7.3	Adverse Events Leading to Death	ITT Population
16.2.7.4	Adverse Events Leading to Study Treatment Discontinuation	ITT Population
16.2.8.1	Pregnancy Test Results for Female Subjects of Childbearing Potential	ITT Population
16.2.8.2	Visual Acuity (logMAR)	ITT Population
16.2.8.3	Slit-Lamp Biomicroscopy and Punctum Examination	ITT Population
16.2.8.4	Intraocular Pressure (mmHg)	ITT Population
16.2.8.5	Dilated Fundus Examination	ITT Population
16.2.8.7	Comments	ITT Population
16.2.8.8	Digital Photographs/Videos	ITT Population

19. Figures

Figure Number	Title	Population
14.2.1.1	Mean +/- SE Ocular Itching	ITT Population with Multiple Imputation (MCMC)
14.2.1.2	Change from Baseline in Ocular Itching (Mean +/- SE)	ITT Population with Multiple Imputation (MCMC)
14.2.1.3	Mean +/- SE Ocular Itching	ITT Population with Observed Data Only
14.2.1.4	Change from Baseline in Ocular Itching (Mean +/- SE)	ITT Population with Observed Data Only

20. Appendix A

Ora Calibra[™] Conjunctival Allergen Challenge Ocular Itching Scale

Itching:

0 = None

- **0.5** = An intermittent tickle sensation possibly localized in the corner of the eye
- **1.0** = An intermittent tickle sensation involving more than just the corner of the eye
- **1.5** = An intermittent all-over tickling sensation
- 2.0 = A mild continuous itch (can be localized) without desire to rub
- 2.5 = A moderate, diffuse continuous itch with desire to rub
- 3.0 = A severe itch with desire to rub
- **3.5** = A severe itch improved with minimal rubbing
- 4.0 = An incapacitating itch with an irresistible urge to rub

0.5 unit increments ARE allowed

Ora Calibra[™] Conjunctival Allergen Challenge Eyelid Swelling Scale

Eyelid Swelling:

- 0 = None
- **1.0** = **Mild** Detectable swelling of lower and/or upper lid
- 2.0 = Moderate Definite swelling of lower and/or upper lid
- **3.0** = **Severe** Swelling of lower and/or upper lid to the point that there is a decrease in the space between your upper and lower lids

0.5 unit increments are NOT allowed

Ora Calibra[™] Conjunctival Allergen Challenge Tearing/Watery Eyes Scale

Tearing/Watery Eyes:

- 0 = None/Normal
- 1 = Mild A noticeably increased moistening of your eye
- 2 = Moderate Your eye feels "full" of water; your lashes feel a little wet
- **3** = **Severe** Feels like tears might drip down your face; very wet lashes
- 4 = Very Severe Tears are dripping down your face

0.5 increments are NOT allowed

Ora proprietary scales – Not for distribution without permission

Subject-Evaluated Nasal Symptoms

Ora Calibra[™] Rhinorrhea Scale

Rhinorrhea (Runny Nose):

- 0= None
- 1= Mild (sensation of nasal mucus flowing down nasal passage; no discharge present)
- **2= Moderate** (may be associated with post nasal drip; nasal mucus flow more pronounced; will need to blow nose soon)
- **3= Moderate/Severe** (nasal mucus discharge requiring occasional wiping with Kleenex)
- **4= Severe** (uncontrolled nasal discharge; requiring frequent wiping and blowing nose)

0.5 unit increments ARE NOT allowed.

Ora Calibra[™] Nasal Pruritus Scale

Nasal Pruritus (Itchy Nose):

0= None

- **1= Mild** (An intermittent tickle sensation)
- 2= Moderate (A mild continuous itch)
- **3= Moderate/Severe** (A severe itch with desire to rub)
- **4= Severe** (Incapacitating itch with an irresistible urge to rub)

0.5 unit increments ARE NOT allowed.

Ora Calibra[™] Ear or Palate Pruritus Scale

Ear or Palate Pruritus (Itchy Ear or Palate):

0= None

- 1= Mild (An intermittent tickle sensation)
- **2= Moderate** (A mild continuous itch)

3= Moderate/Severe (A severe itch with desire to rub)

4= Severe (Incapacitating itch with an irresistible urge to rub)

0.5 unit increments ARE NOT allowed.

Ora Proprietary Scales - Not for distribution without permission

Ora Calibra[™] Nasal Congestion Scale

Nasal Congestion:

0= None (No breathing difficulty)

- 1= Mild (Some sensation of blockage)
- **2= Moderate** (Partial Blockage)
- 3= Moderate/Severe (Significant blockage but can still breathe through nose)
- 4= Severe (Cannot breathe through nose at all)

0.5 unit increments ARE NOT allowed.

Investigator-Evaluated Signs (Ocular)

Ora Calibra[™] Ocular Hyperemia Scale

Regional Redness: Hyperemia (ciliary, conjunctival, and episcleral). All evaluated separately by an Investigator with the slit lamp

0 = None

1 = **Mild** – Slightly dilated blood vessels; color of vessels is typically pink; can be quadrantal

2 = **Moderate** – More apparent dilation of blood vessels; vessel color is more intense (redder); involves the majority of the vessel bed

3 = **Severe** – Numerous and obvious dilated blood vessels; in the absence of chemosis the color is deep red, may be less red or pink in presence of chemosis, is not quadrantic

4 = Extremely Severe – Large, numerous, dilated blood vessels characterized by unusually severe deep red color, regardless of grade of chemosis, which involves the entire vessel bed

0.5 unit increments ARE allowed

Ora Calibra[™] Chemosis Scale

Chemosis:

0 = None

1.0 = Detectable only by slit lamp beam; definite separation of conjunctiva from sclera

2.0 = Visible in normal room light; more diffuse edema

3.0 = Conjunctival billowing at the limbus; very diffuse and noticeable

4.0 = Severe overall billowing of conjunctiva

0.5 unit increments ARE allowed

Ora Proprietary Scales – Nor for distribution without permission
